## **9.5.10 Exposure and Compliance**

### **9.5.10.1 Investigational Product Exposure and Compliance**

The extent of exposure to the IP in each treatment group will be summarized by total number of days of exposure and total number of injections. Percentage of compliance for a participant will be defined as the number of injections administered divided by the total number of injections the participant was expected to take during the treatment period. A participant will be considered compliant with the dosing regimen if the participant received  $\geq 75\%$  of the expected number of injections while enrolled in the study.

### **9.5.10.2 Background Medication Compliance**

Compliance for protocol-specified background medication will be calculated for each participant. Percentage of compliance is defined as the number of days when the participant is compliant to the prescribed background medication regimen divided by the number of days the participant stays in the treatment period.

## **9.5.11 Other Analyses**

Summary statistical analyses will be provided for demographics, baseline disease characteristics, medical history, and other characteristics.

Participant disposition will be summarized by treatment or by treatment sequence for each period and include the number of participants in the ITT Analysis Set who completed or withdrew from treatment for each period, as well as the number of participants in each analysis set.

The number of participants who withdrew from IP and withdrew from study will be summarized by treatment or by treatment regimen for each period and the reason for withdrawal.

Medical history will be coded according to the latest version of MedDRA and will be summarized by SOC and preferred term.

The number and percentage of participants with prior and concomitant medications will be tabulated by Anatomical Therapeutic Chemical Classification System of WHO Drug Global dictionary, preferred term, and actual treatment received (or treatment sequence). A medication's usage will be considered concomitant if it was started or continued after the first administration of the IP. If the start date is missing, it will be assumed that the medication was used concomitantly. Details on handling partial dates (ie, year or only year and month) will be described in the SAP.

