### **5.1 Inclusion Criteria**

Each participant must meet all of the following criteria to be enrolled in this study:

1. Adult participants  $\geq 18$  years of age at time of signing the informed consent form (ICF) and adolescent participants  $\geq 12$  to  $< 18$  years of age and weighing  $\geq 40$  kg at Visit 1. Legal age may vary depending on regulations of each country and country standards will be followed.
2. Physician-diagnosed CRS with bilateral NP.

3. Prior treatment with SCS for CRS or CRSwNP within the last 2 years (or a medical contraindication or intolerance to SCS), prior surgery for NP, or both.
4. Endoscopic bilateral NPS score of at least 5 out of 8, with a minimum score of 2 in each nasal cavity performed at screening (Visit 1) and baseline (Visit 3).
5. Ongoing symptoms for at least 8 weeks prior to study entry (screening [Visit 1]), including:
  - a. Nasal congestion with moderate or severe symptom severity (score 2 or 3) at screening (Visit 1) (single day for Visit 1) and a weekly average severity score of at least 1 (range 0 to 3) at randomization (average of the 14 days prior to Visit 3 [baseline]), and
  - b. At least one other symptom, such as, but not limited to, partial loss of smell (hyposmia), total loss of smell (anosmia), or anterior or posterior rhinorrhea.
6. Participants who have concomitant asthma must be stable in the 3 months prior to screening using permitted regular asthma treatment.
7. Participants must complete their eDiaries at least 4 out of 7 days every week in the 2 weeks prior to randomization visit (Visit 3 [baseline]).
8. Women of childbearing potential (WOCBP) must use at least 1 highly effective contraceptive or a combination of 2 effective contraceptive methods consistent with local regulations regarding the methods of contraception for those participating in clinical studies. WOCBP and women not of childbearing potential (WNOCBP) may participate in this study. See [Appendix 15.1](#) for definitions and additional requirements related to contraception.

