## **6.10 Prior, Concomitant, and Rescue Medications and Therapies**

Any medication (including vaccines and over-the-counter or prescription medicines, recreational drugs, vitamins, and/or herbal supplements) that the participant is taking at the time of screening or subsequently during the study enrollment or receives during the study must be recorded, including the following:

- Identity (specific to product name if a combination drug product), spelled correctly.
- Reason for use.
- Dates of administration, including start and end dates.
- Dosage information, including dose, frequency, and route of administration.

The medical monitor should be contacted if there are any questions regarding prior or concomitant therapy.

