### **6.10.2.1 Prohibited Concomitant Medications**

In addition to the medications listed in [Section 5.2](#), the following will be prohibited during the study:

- Daily aspirin for treatment of AERD (aspirin is allowed as needed for pain relief or other indications).
- Intranasal antihistamines or combination intranasal corticosteroid antihistamines (eg, azelastine, olopatadine/mometasone furoate).
- Any biologic not approved for CRSwNP according to local regulatory authorization.
- Systemic antimicrobials >10 days.
- Nasal saline lavage with antibiotics and/or nasal saline lavage with corticosteroids (>10 days).
- Any systemic immunosuppressive treatment.
- Allergy immunotherapy (SCIT/SLIT), except if initiated more than 6 months prior to screening (Visit 1) and the dose is stable 3 months prior to screening (Visit 1) with no change in dose during the study.
- Use of INCS (other than mometasone furoate).
- Long-term course (>7 days) of SCS for any indications.

- Use of SCS between screening (Visit 1) and baseline (Visit 3) (screening and run-in period).
- Fluticasone propionate.
- Oral decongestants for any length of time to treat CRSwNP or oral decongestants >5 days to treat an acute adverse event.
- Intranasal decongestants, except as single use for nasal endoscopy.
- Leukotriene receptor antagonists.
- Live or live attenuated vaccines.

Participants who take any prohibited medications must discontinue from IP, but can remain in the study, unless the investigator decides to withdraw the participants from the study.

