## 8.1.2 Demographics, Medical History, and Prior Medication Procedure

Demographic information to be obtained will include age, sex, race, and ethnicity as described by the participant, and substance use history. The scientific rationale for this collection is the need to assess variable response in safety and/or efficacy based on race or ethnicity. Substance use history will also be collected. Only if all relevant data are collected can this assessment be made.

Medical history to be obtained will include determining whether the participant has any significant conditions or diseases relevant to the disease under study that stopped at or prior to signing the ICF. Ongoing conditions are considered concurrent medical conditions.

Medication history (ie, prior medications) to be obtained includes any medication relevant to eligibility criteria and safety evaluation stopped at or within the specified period of time prior to screening (Visit 1).

Physical examination (including height) is described in [Section 8.3.3](#) and [Section 8.3.4](#).

Assessment of vital signs (including weight) is described in [Section 8.3.5](#).

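### A missing start date makes a medication concomitant even when its recorded stop date is before the first dose, against the protocol's own definition (minor)

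*Protocol*

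**What the plan says.** Protocol section 9.5.11 (Other Analyses) plans a tabulation of prior and concomitant medication by ATC class and preferred term. Three consecutive sentences set the classification.

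1. The definition: a medication's use "will be considered concomitant if it was started or continued after the first administration of the IP".
2. The rule for a missing start: "If the start date is missing, it will be assumed that the medication was used concomitantly".
3. The deferral: "Details on handling partial dates (ie, year or only year and month) will be described in the SAP".

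Two other sections decide which records the rule can reach. Section 6.10 lists among the items to record "Dates of administration, including start and end dates", so stop dates are collected. Section 8.1.2 takes as medication history "any medication relevant to eligibility criteria and safety evaluation stopped at or within the specified period of time prior to screening", so drugs that ended before the trial are in the database.

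**The concern.** The second sentence does not look at the stop date. If the start is unknown but the drug is known to have ended before the first dose, its status is not in doubt, because it cannot have been used on study. The rule still calls it concomitant.

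Records of this kind are plausible here. One of the qualifying histories in inclusion criterion 3 is "Prior treatment with SCS for CRS or CRSwNP within the last 2 years". Section 6.10.2.1 prohibits systemic corticosteroids (SCS) between screening and baseline, so in a compliant participant a qualifying course had ended before the first dose. An earlier nasal steroid whose start nobody remembers is another ordinary case.

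What is at stake is the accuracy of the medication table. Section 6.10.2.1 prohibits nasal steroids other than mometasone during the study, and section 6.10.3 lists SCS as rescue. A finished pre-study course shown as concomitant could be read as prohibited or rescue use that the database itself contradicts.

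**Working it through.** The plan states no figure on this point, so there is none to reproduce. The check applies sentences 1 and 2 of section 9.5.11 to each combination of start and stop date.

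| Start date | Stop date | Definition (sentence 1) | Missing-start rule (sentence 2) | Agreement |
|---|---|---|---|---|
| Known, before first dose | Before first dose | Prior | Does not apply | – |
| Known, before first dose | After first dose, or ongoing | Concomitant | Does not apply | – |
| Known, after first dose | Any | Concomitant | Does not apply | – |
| Missing | After first dose, or ongoing | Concomitant | Concomitant | Yes |
| Missing | Missing | Cannot be decided | Concomitant | No conflict; a cautious default |
| Missing | Before first dose | Not concomitant | Concomitant | **Conflict** |

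The two sentences conflict in one cell only: start wholly missing, stop known and before the first dose.

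Three further checks:

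- **Can the cell be identified in the data?** Yes. Section 6.10 records end dates, and section 6.10.2 also asks for a discontinuation date.
- **Is the rule left to the statistical analysis plan?** No. The deferral covers a start known to the year, or to the year and month. The wholly missing start is settled in the protocol text.
- **How many records fall in the cell?** The count is the number of finished pre-study records multiplied by the share with no start date at all. The protocol gives neither, so no count or range can be derived from it.

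If the missing-start rule carried an exception for a stop before the first dose, the last row would become prior. The other five rows would stay as they are.

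**The case against.** The strongest defence is that sentence 2 is a cautious default for unknown timing, that sentence 1 still governs, and that section 9.5 leaves data conventions to the statistical analysis plan. Part of this stands. The default is sensible when the stop date is also missing. But the sentence is unconditional as written, and a programmer following it would flag a drug that the recorded stop date rules out. Section 9 says that changes from the planned analyses will be documented in the statistical analysis plan, so a correction there would itself be such a change.

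It can also be said that undated steroid courses should be uncommon. To satisfy a two-year window a site must place the course in time, usually at least to the year, and a year-only start is a partial date outside this rule. Nor does every participant bring such a course. Criterion 3 is also met by prior polyp surgery alone, or by a contraindication or intolerance to SCS. Section 9.3 limits adults without prior surgery to about 255 of 510, which leaves about 510 − 255 = 255 or more with prior surgery. Both arguments stand and limit the likely number of records.

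A reader might go further and infer that pre-study SCS courses become rescue events or intercurrent events, dilute the hazard ratio and cost power. The documents do not support that:

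- Section 9.5.11 ties the flag to the medication table and to nothing else.
- Section 9.5.4 analyses the first rescue event during the study treatment period.
- Section 8.2.7 has the date and dosing of SCS recorded, and the Schedule of Activities (Table 1-1) has a row for rescue medication that starts at Visit 4, separate from the screening row for prior treatments.
- Table 9-1 separates short-term from long-term SCS by dose and days of use, and section 9.6 replaces only data collected after the event. Both need dates.
- A time-to-event analysis needs an event time. A record with no start date supplies none, and the protocol has no rule that would impute one.

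**Conclusion.** The rule is wrong as written, in one cell. A drug with a wholly missing start date and a recorded stop before the first dose is classed as concomitant, contrary to the definition in the sentence before it. The consequence is miscounting in one descriptive table.

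The size cannot be stated from the protocol. Medication history is taken at screening, before randomisation, so missing start dates in it should be balanced between the arms in expectation. The likely result is inflated counts in all arms, not a distorted comparison.

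No effect on the co-primary endpoints, the rescue endpoint or the handling of intercurrent events is shown. The conclusion rests on the literal wording of section 9.5.11 and on stop dates being collected as section 6.10 requires. Severity is minor.

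**What to change.** Replace the missing-start sentence in section 9.5.11, or record the change in the statistical analysis plan before unblinding, along these lines:

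> A medication with a missing start date will be assumed concomitant unless its stop date (complete, or partial but sufficient to decide) is before the first administration of IP, in which case it is prior.

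The default stays where timing is truly unknown, and only the conflicting cell changes class. The cost is one sentence and one condition in the derivation code, with no new data.

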## 9.6 Handling of Missing Data

The primary method of handling ICEs and missing data for primary and key secondary endpoints will be aligned with the primary estimand.

- Data collected after treatment discontinuation or short-term use of SCS will be included in the analysis.
- For participants who undergo NP surgery, change to another biologic therapy or use long-term SCS or nasal saline lavage with corticosteroids, data collected after the ICEs will be set to missing and imputed by the worst possible score.

Multiple imputation will be used to handle the remaining missing data. The SAS PROC MI will be used to conduct the multiple imputation. Each complete dataset will be analyzed with the specified analysis. The results from these analyses will be combined into a single inference.

## 9.7 Interim Analyses

[figure not shown]
No interim analysis will be performed.

## 9.8 Multiple Comparisons and Multiplicity

Multiplicity adjusted analyses will be performed on the co-primary and key secondary objectives for the adult participants to control the overall family-wise Type I error rate at a 2-sided alpha level of 0.01. The graphical multiple testing procedure described in [Bretz et al. \(2009, 2011\)](#) will be used. This approach is a closed testing procedure; hence, it strongly

controls the family-wise error rate across all hypotheses (Alosh et al 2014). Figure 9-1 illustrates the current graphical testing procedure. Details of the final graphical testing scheme (including testing order, interrelationships, Type I error allocation for the co-primary and key secondary objectives, and the associated propagation) will be prespecified in the SAP prior to database lock. Unless otherwise specified, there will be no adjustment for multiple comparisons for any other analyses outside the co-primary and key secondary objectives.

**Figure 9-1 Graphical Approach to Control Type I Error Rate for the Adult Participants**

### 9.9 External Data Monitoring Committee

Not applicable to this study.

### 10 Data Quality Assurance

This study will be conducted according to the ICH E6(R2) risk and quality processes described in the applicable procedural documents. The quality management approach to be implemented in this study will be documented and will comply with the current ICH guidance on quality and risk (ICH Q9[R1]). The sponsor assumes accountability for actions delegated to other individuals, eg, contract research organizations (CROs).

Quality tolerance limits will be predefined to identify systematic issues that can impact participant safety and/or reliability of study results. These predefined parameters will be

monitored during the study and important excursions from the quality tolerance limits and remedial actions taken will be summarized in the clinical study report.

## **10.1 Data Management**

As part of the responsibilities assumed by participating in the study, the investigator agrees to maintain adequate case histories for the participants treated as part of the research under this protocol. The investigator agrees to maintain accurate eCRFs and source documentation as part of the case histories. These source documents may include laboratory reports.

Data will be collected via eCRFs, and data must be entered into eCRFs in English. Designated study site staff must complete eCRFs as soon as possible after a participant visit, and the forms should be available for review at the next scheduled monitoring visit. All eCRF entries, corrections, and alterations must be made by the investigator or other authorized site staff. Discrepancies in the data will be brought to the attention of the clinical team and study site staff, if necessary. Resolutions to these issues will be reflected in the database. An audit trail within the system will track all changes made to the data.

The investigator must permit study-related monitoring, audits, IRB/IEC review, and regulatory agency inspections and provide direct access to source data documents.

Monitoring details describing strategy (eg, risk-based initiatives in operations and quality such as Risk Management and Mitigation Strategies and Analytical Risk-Based Monitoring), methods, responsibilities, and requirements, including handling of noncompliance issues and monitoring techniques are provided in the monitoring plan.

The sponsor, or designee, is responsible for the data management of this study including quality checking of the data.

Clinical data management will be performed in accordance with applicable standards and data cleaning procedures to ensure the integrity of the data, eg, removing errors and inconsistencies in the data. AE terms will be coded using MedDRA and concomitant medications will be coded using the WHO Drug Global dictionary.

### 10.1.1 Electronic Data Capture of Clinical Outcome Assessment

All PROs conducted at the study site will be captured on an electronic tablet during study site visits. All PRO assessments captured away from the study site will be captured in the participants' eDiaries.

The tablets at the study site will be programmed to capture the following PROs, which will be completed by participants during study site visits according to the SoA ([Table 1-1](#)):

- VAS of CRS severity ([Section 8.2.9](#))
- PGI-S scales ([Section 8.2.17](#))
- PGI-C scales ([Section 8.2.17](#))
- SNOT-22 ([Section 8.2.10](#))
- ACQ-6 ([Section 8.2.12](#), in asthma participants only)
- PROMIS Short Form v1.0 – Anxiety 8a ([Section 8.2.16.1](#))
- PROMIS Short Form v1.0– Depression 8a ([Section 8.2.16.2](#))
- WPAI+CIQ:CRSwNP ([Section 8.2.15](#))
- EQ-5D-5L ([Section 8.2.14](#))

The PROs will be completed by participants using an on-site tablet in the following order: VAS of CRS severity, PGI-S: nasal congestion, PGI-S: loss of smell, PGI-S: postnasal drip, PGI-C: nasal congestion, PGI-C: loss of smell, PGI-C: postnasal drip, SNOT-22, ACQ-6, PROMIS Anxiety, PROMIS Depression, WPAI+CIQ:CRSwNP, and EQ-5D-5L.

The eDiaries will be programmed to capture the following PROs and other study data:

- NCS ([Section 8.2.1](#))
- Loss of smell ([Section 8.2.5](#))
- Postnasal drip ([Section 8.2.6](#))

- Loss of taste ([Section 8.2.8](#))
- Facial pain/pressure ([Section 8.2.8](#))
- Rhinorrhea ([Section 8.2.8](#))
- IP dosing diary ([Section 6.1.2](#))
- Background medication dosing diary ([Section 6.10.2.2](#))

The PROs should be completed by the participant in their eDiary in the following order: NCS, loss of smell, postnasal drip, loss of taste, facial pain/pressure, and rhinorrhea.

## 11 Ethics

The study will be performed in accordance with the ethical principles that have their origin in the Declaration of Helsinki, ICH Good Clinical Practice (GCP), and all applicable regulations. The study will be conducted in the EU under Regulation (EU) No. 536/2014.

### 11.1 Institutional Review Board or Independent Ethics Committee

Federal regulations and the ICH guidelines require that approval be obtained from an IRB/IEC before human participants participate in research studies. Before study onset, the protocol, ICF, advertisements to be used for the recruitment of participants, and any other written information regarding this study to be provided to the participant must be approved by the IRB/IEC. Documentation of all IRB/IEC approvals and of the IRB/IEC compliance with ICH harmonised tripartite guideline E6(R2): GCP will be maintained by the study site and will be available for review by the sponsor or its designee.

All IRB/IEC approvals should be signed by the IRB/IEC chairman or designee and must identify the IRB/IEC name and address, the clinical protocol by title or protocol number or both, and the date of approval or a favorable opinion was granted.

The investigator is responsible for providing written summaries of the progress and status of the study at intervals not exceeding 1 year or otherwise specified by the IRB/IEC. The investigator must promptly supply the sponsor or its designee, the IRB/IEC, and, where applicable, the institution, with written reports on any changes significantly affecting the conduct of the study or increasing the risk to participants.

## **11.2 Ethical Conduct of the Study**

The study will be performed in accordance with the ethical principles that have their origin in the Declaration of Helsinki, ICH GCP, and all applicable regulations.

## **11.3 Participant Information and Consent**

A written informed consent in compliance with all countries participating in the study shall be obtained from each participant before entering the study or performing any unusual or nonroutine procedure that involves risk to the participant. A study-specific master ICF will be provided by the sponsor to study sites. If any institution-specific modifications to study-related procedures are proposed or made by the study site, the consent should be reviewed by the sponsor or its designee or both before IRB/IEC submission. Once reviewed, the ICF will be submitted by the investigator to his or her IRB/IEC for review and approval before the start of the study. If the ICF is revised during the course of the study, all active participants must be reconsented by signing the revised ICF.

Before recruitment and enrollment, each prospective adult participant or parental/legal guardian of an adolescent participant will be given a full explanation of the study, be allowed to read the approved ICF, and have any questions answered. Once the investigator is assured that the adult participant or parental/legal guardian of an adolescent participant understands the implications of participating in the study, the adult participant or parental/legal guardian of an adolescent participant will be asked to give consent to participate in the study by signing the ICF. The authorized person obtaining the informed consent also signs the ICF.

Adolescent participants must also understand the nature of the study and sign an informed assent document prior to receiving any study-related procedures as required by local regulations.

The ICF will contain a separate section that addresses the use of remaining mandatory samples for optional exploratory research (if applicable) and explain/address the exploratory research portion of the study. Participant medical records need to state that written informed consent was obtained.

The investigator shall retain the signed original ICFs and give a copy of the signed original form to the participant.

